⁶Hyperinsulinemic-euglycemic clamp: The glucose clamp is the gold standard for measurement of insulin sensitivity and will be performed as previously described by our group (3, 15, 27, 29). After an overnight 8-hour fast, an intravenous catheter will be placed in the vein for infusion of insulin and glucose. A second catheter will be placed in the vein of the contra-lateral arm for blood withdrawal. After baseline blood is collected, a primed (210 mg/m²), continuous (2 mg/min/m²) infusion of U13C glucose will be initiated for assessment of endogenous glucose production. A 2-step euglycemic clamp will be started with a 2-hour infusion of insulin (Humulin-R) at 10-30 mU/m²/min, followed by 2 hours at 80-100 mU /m²/min. Plasma glucose will be measured at ~5 min intervals via NOVA StatStrip Glucose Meter. Plasma glucose will be allowed to either decrease to ~90 mg/dl or will be increased to ~90 mg/dl in each participant depending on the fasting blood glucose levels. Euglycemia (~90 mg/dL) will be maintained with a variable 20% dextrose infusion enriched with U13C glucose. Rates of glucose disposal (M) and endogenous glucose production (EGP) will be calculated by non-steady-state equations based on plasma U13C glucose enrichment determined by gas chromatography mass spectrometry. A baseline blood sample will be collected prior to -30 mins. Then three blood samples will be collected for determination of plasma insulin, free fatty acid (FFAs), C-Peptide, and glucose concentrations prior to the insulin infusion, and at the beginning of each steady state and every 10 minutes during the two steady state portions of the clamp which will last approximately 4 hours from the time at which the insulin infusion is initiated (-30min, -20min, -10min, 0min, +30min, +60min, +100min, +110min, +120min, +220min, +230min, and +240min) . Participants will complete a 24-hour urine collection on days where hyperinsulinemic-euglycemic clamps are run. Total blood volume during this procedure will be approximately 192 mls. Bedrest ends after the completion of the hyperinsulinemic-euglycemic clamp on Day 10.

Calculations: Hepatic glucose production is expected to be completely suppressed at this level of insulin, even in diabetic subjects. In this case, peripheral glucose uptake (R_d) should equal the glucose infusion rate (GINF) during steady state (the last 30 minutes of each step of the clamp) after correction for urinary glucose loss.

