That is: - R_d = Steady State GINF - urinary glucose loss

Insulin sensitivity (S_i) will be calculated using the formula: S_i = R_d / (steady state insulin level - basal insulin level) where steady state insulin equals the average insulin concentration during the last 40 minutes of the clamp and basal insulin equals the average insulin level in the 30 minutes before starting the insulin infusion.

Fasting and insulin-suppressed FFA [IS-FFA] will be measured with an ultrasensitive FFA assay from Wako. Glucose disposal rate [GDR] will be expressed as mg/kg FFM [DEXA]/minute.

Metabolic flexibility of substrate oxidation

Before and during the steady state of the clamp, we will measure substrate oxidation using a MAX I Metabolic Cart (AEI Technologies, Pittsburgh, PA) to measure ‘metabolic flexibility’ as described by Kelley and Mandarino (62).

⁷A blood collection will be done to test the participant’s hemoglobin and hematocrit levels on Day 7 and Day 10. If the hemoglobin level is < 10.0 g/dL for females or < 11.0 g/dL for males on either day, the medical provider may repeat the tests and/or withdraw the participant from the study.

⁸Administration of D₂O. 25ml of 99% D₂O will be consumed 2x/day for the first week following bed rest and 25 ml once a day for the next 3 weeks, with the last dose being given the day before week 4, visit 16. This regimen will provide a stable, continuous precursor pool enrichment of body water.

⁹A number of health questionnaires will be administered following bed rest, including: Life Space, Lifestyle, Functional Status, Pittsburgh Fatigability Scale.

¹⁰Resting Metabolic Rate/Respiratory Quotient (RMR/RQ) will be determined that morning in the fasting state.

¹¹An orthostatic hypotension assessment will be completed once participants become ambulatory. This will be completed by measuring blood pressure while in lying down, sitting, and standing positions. The assessment will be completed to ensure participant safety prior to being discharged from TRI.

Phase IV-Ambulatory/Exercise Recovery Program

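### The clamp note applies an R_d formula with no endogenous glucose production term to both insulin steps, although the same note measures that production with a tracer

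*Protocol*

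**What the plan says.** All of this is in the Protocol, Phase III – Bed Rest, footnote 6 (Hyperinsulinemic-euglycemic clamp) and its Calculations.

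- **Two insulin levels.** The low step is described so: "A 2-step euglycemic clamp will be started with a 2-hour infusion of insulin (Humulin-R) at 10-30". Rates are in mU/m²/min. A second two-hour step runs at 80-100.
- **A tracer.** After baseline blood, a primed continuous "infusion of U13C glucose will be initiated for assessment of endogenous glucose production". Euglycemia "will be maintained with a variable 20% dextrose infusion enriched with U13C glucose".
- **Tracer-based disposal.** "Rates of glucose disposal (M) and endogenous glucose production (EGP) will be calculated by non-steady-state equations" from plasma enrichment.
- **Infusion-based disposal.** The Calculations then state: "Hepatic glucose production is expected to be completely suppressed at this level of insulin, even in diabetic subjects". If that holds, the rule for uptake is this: "peripheral glucose uptake (R_d) should equal the glucose infusion rate (GINF) during steady state (the last 30 minutes of each step of the clamp". Glucose lost in urine is to be subtracted, and the formula is written as "R_d = Steady State GINF - urinary glucose loss".
- **Derived indices.** S_i is R_d divided by the rise in insulin over basal, with the steady-state insulin averaged over the final 40 minutes of the clamp. A glucose disposal rate (GDR) is reported per kg of fat-free mass.
- **Two clamps per participant.** One closes bed rest: "Bedrest ends after the completion of the hyperinsulinemic-euglycemic clamp on Day 10". The other is at week 4, visit 16 of the Phase IV schedule.

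**The concern.** The note holds two calculations of disposal and does not say which applies at which step. One measures EGP. The other sets it to zero. The zero-EGP premise is written for one insulin level, yet the formula built on it is stated for each step, so it takes in the 10-30 mU/m²/min step, where complete suppression is harder to presume.

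If EGP is not fully suppressed at the low step, an R_d taken from the infusion rate confuses liver output with peripheral uptake. A change in hepatic suppression between the two clamps could then be read as a change in peripheral uptake, in a study whose interest is muscle. A smaller gap sits beside this: the insulin term of S_i belongs to the high step, but its R_d term is defined for each step and tied to neither.

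**Working it through.** The Protocol states no sample size, power or alpha for the clamp, so there is no figure to reproduce. The check is a mass balance plus the timing of the windows.

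**1. Insulin levels (footnote 6).** The high rate is 80/30 = 2.7 to 100/10 = 10 times the low rate. A single insulin level cannot describe both steps.

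**2. Windows (footnote 6).**

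| Quantity | Window (min) | Scheduled samples in it |
|---|---|---|
| R_d, low step (0-120), last 30 min | 90-120 | +100, +110, +120 |
| R_d, high step (120-240), last 30 min | 210-240 | +220, +230, +240 |
| S_i insulin term, last 40 min of clamp | 200-240 | +220, +230, +240 |

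The low step is thus a sampled steady-state window, and the S_i insulin term lies wholly in the high step.

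**3. Mass balance.** At steady state, ignoring the small separate tracer infusion (2 mg/min/m²):

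- R_d = GINF + EGP − urinary loss
- Protocol formula: R_d = GINF − urinary loss
- Difference = EGP

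The two agree only at EGP = 0. The difference is approximate, because of the tracer infusion and because steady state is never perfect.

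**4. Relative size (assumed inputs; the documents give no EGP, GINF or R_d value).** Let G = GINF − urinary loss and e = EGP/G. True R_d is G(1 + e), the formula returns G, and the understatement is e/(1 + e).

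| Assumed e | Understatement of R_d |
|---|---|
| 0 | 0% |
| 0.10 | 0.10/1.10 = 9% |
| 0.25 | 0.25/1.25 = 20% |
| 0.50 | 0.50/1.50 = 33% |

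A fixed amount of EGP matters less where disposal is higher. With an assumed EGP of 0.5 mg/kg/min, the shortfall is 0.5/2 = 25% at a true R_d of 2 mg/kg/min, and 0.5/8 = 6% at 8.

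**5. Effect on the randomised comparison (hypothetical, mg/kg/min).** Hold true R_d at 3 in both arms at both clamps and start both arms at EGP 0.50, so the formula gives 3 − 0.50 = 2.50 in each.

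- EGP falls to 0.25 in both arms: both move to 3 − 0.25 = 2.75. The false EX–CON difference in change is 0.25 − 0.25 = 0.
- EGP falls to 0.25 in EX only: EX changes by +0.25 and CON by 0. The false difference is 0.25.

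A false group difference therefore needs a change in EGP that differs between arms.

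**The case against.** The strongest reply is that the Protocol already has the right calculation. Tracer-based M and EGP are promised without condition. The infusion-rate rule is the hedged one: suppression is only expected, and the equality is offered for that case. Read together, the tracer gives disposal and the infusion rate is a simplification for when suppression is complete. This largely stands. A reader might infer that the Protocol has no disposal rule for incomplete suppression; it does. What remains is that the simplification is expressly extended to each step, and nothing says which value is used where.

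A reader might also infer that GDR is the affected figure. The text does not show that. GDR shares its name with the tracer-based disposal rate M, whereas the Calculations call their quantity peripheral uptake, so M is the more natural reading.

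Third, S_i is the only index expressly built from R_d, and its insulin term already points to the high step. A matched numerator would be high-step R_d. No endpoint or analysis names a low-step R_d. That is correct and limits the consequence, though the numerator is still not tied to a step.

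Last, the choice of estimator for a non-primary assay could be left to a separate analysis plan, which is not shown. The point here is not a missing detail, however. The Protocol itself states a formula and a scope, and that scope does not fit its own premise or its tracer plan.

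**Conclusion.** The point holds as an inconsistency of low priority. The formula without EGP is given for both steps on a premise written for one, beside a tracer plan that would measure the omitted term. Where EGP is not zero, the formula understates uptake by about that EGP, most importantly at the low step.

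The size is unknown and may be zero. The 9%, 20% and 33% are illustrations at assumed ratios and should not be read as estimates of bias in this trial; nothing in the documents says how much EGP persists at 10-30 mU/m²/min.

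Two wider conclusions are not supported. An EGP change shared by both arms would not create a false EX–CON difference in R_d. Nor is the primary analysis at risk: the named primary outcomes are leg lean mass, protein synthesis rate and mitochondrial respiration, and the sample size rests on leg lean mass and OXPHOS protein expression. What is touched is insulin sensitivity, a listed but non-primary outcome, and the exploratory look in the Statistical Analysis Plan section at how change in insulin resistance relates to protein synthesis and mitochondrial function.

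**What to change.** Reword the Calculations in footnote 6, without touching the clamp procedure:

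1. Replace the each-step wording so that the GINF-minus-urinary-loss rule applies at most to the high step, and say that the suppression premise refers to that step.
2. At the low step, use the tracer-derived disposal and EGP already planned, for all participants and at both clamps. Fix the high-step estimator in advance too, not according to the EGP observed.
3. State that the R_d in S_i is the high-step R_d, to match its insulin term.
4. State that GDR is the tracer-based M, or name the estimator used.

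The cost is a few sentences. The tracer data are already to be collected, so no new sample or procedure is needed.

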Exercise Recovery. The **exercise recovery program** will be supervised by a certified exercise physiologist and will take place at the TRI exercise training facility. Exercise compliance will be monitored carefully. We are examining the muscle specific effects of the recovery exercise program on the muscle groups of interest. We will use an exercise recovery program that has demonstrated substantial increases in quadriceps muscle size and strength in elderly people (37, 40, 105). During the 4 weeks of recovery, participants will perform a combination of aerobic and resistance exercise training with a certified exercise physiologist 3 days per week at the TRI exercise training facility. Exercise compliance and adherence will be monitored carefully. Aerobic training will be 30 minutes of brisk walking, jogging, cycle ergometry and will be at 60-80% of post bed rest VO₂max peak HR. Participants will wear a Heart Rate Monitor during Aerobic exercise sessions. Walking will be the primary mode of aerobic exercise given its widespread popularity and ease of administration across a broad segment of the older adult population. Three sets of 8–12 repetitions of each resistance exercise will be performed to target the major lower body muscle groups, including the vastus lateralis of the quadriceps.

Ambulatory Recovery. Participants in the ambulatory recovery group will not receive any exercise intervention or advice on exercise. Rather these participants will return to their regular daily routine that they engaged in prior to the bed rest intervention.

Participants in both Exercise and Ambulatory Recovery will be admitted to TRI the evening before Week 4 / Visit 16 for an overnight stay. The participants will be served dinner and type 2 diabetics will be asked to bring their own home glucometer to test glucose.

The following table summarizes the schedule of assessment during Ambulatory/Exercise Recovery Phase. Descriptions of assessments can be found above (Phase III).

Week Visit	Week 1				Week 2				Week 3				Week 4			
	1	2	3	4	5	6	7	8	9	10	11	12	13	14	15	16
Day of Week	F	M	T	Th	F	M	T	Th	F	M	T	Th	F	M	T	F
Window Days	+1	+1	+1	+1	+1	+1	+1	+1	+1	+1	+1	+1	+1	+1	+1	+3
Fasting Muscle Biopsy/Blood Draw ¹				X ^{**}				X ^{**}				X ^{**}				X ^{**}
Fasting Adipose Biopsy ² (optional)																X ^{**}
24-Hour Urine																X ^{**}
Glucose Clamp - 4Hr ⁶ with RMR																X ^{**}
Vital Signs	X*	X*	X*	X ^{**}	X*	X*	X*	X ^{**}	X*	X*	X*	X*	X*	X*	X*	X ^{**}

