Medication/Supplement Intake & Changes	X*	X*	X*	X ^{**}	X*	X*	X*	X ^{**}	X*	X*	X*	X*	X*	X*	X*	X ^{**}
Adverse Events	X*	X*	X*	X ^{**}	X*	X*	X*	X ^{**}	X*	X*	X*	X*	X*	X*	X*	X ^{**}
Metabolic Body Weight ¹⁶				X ^{**}				X ^{**}				X ^{**}		X ^{**}		X ^{**}
BIODEX/Strength Testing												X ^{**}				
Handgrip Strength												X ^{**}				
SPPB												X ^{**}				
Step Test												X ^{**}				
Questionnaires ²													X ^{**}			
DEXA				X ^{**}				X ^{**}				X ^{**}				X ^{**}
MR Assessments (ATPmax/IMCL/IMAT)				X ^{**}				X ^{**}				X ^{**}				X ^{**}

Accelerometer Handout															X*	X[^]
Accelerometer Collection						X*		X[^]								
VO _{2max} Test															X*[^]	
Cardio Exercise Program	X*	X*	X*		X*	X*	X*		X*	X*	X*		X*	X*	X*	
Strength Exercise Program	X*	X*	X*		X*	X*	X*		X*	X*	X*		X*	X*	X*	
Deuterated H ₂ O administration ⁸	X*[^]		X*[^]	X*[^]	X*[^]											
400m Walk Test															X*[^]	

* = only on this visit for exercise cohort

[^] = only on this visit for ambulatory cohort

Phase V – Optional Resistance Training.

Following Phase IV of the study, to expedite complete recovery, subjects may attend three resistance exercise training sessions per week over a four-week period, for a total of 12 visits. Resistance exercise training will include weight training of all major muscle groups. Subjects will perform three sets of eight repetitions at 70-80% of their 1 RM for each exercise, which will include upper body and lower body muscle groups. During all exercise sessions, subjects must be supervised by qualified personnel with the appropriate training to identify if the subject is under any type of distress. Study assessments will also be performed during the 4-week resistance training according to the table below:

Assessment	Resistance Training (Optional)											
	Week 1			Week 2			Week 3			Week 4		
	1	2	3	4	5	6	7	8	9	10	11	12
Vital Signs	X	X	X	X	X	X	X	X	X	X	X	X
Medication/supplement intake and changes	X	X	X	X	X	X	X	X	X	X	X	X
Adverse events	X	X	X	X	X	X	X	X	X	X	X	X
Metabolic Body Weight ¹⁶			X			X			X			X
Resistance Training ¹	X	X	X	X	X	X	X	X	X	X	X	X
BIODEX/Strength Testing	X											X
Handgrip Strength						X						X
SPPB						X						X
Step Test						X						X
Questionnaires ²						X						X
Accelerometer Collection		X										

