Participants will be assigned unique identifiers for study-related records. All precautions will be taken to make sure that only authorized individuals will access participant research records. The collection of sensitive information about participants will be limited to minimum necessary to achieve the aims of the research, so that no unneeded sensitive information will be collected.

Early Withdrawal of Subjects

Investigator Withdrawal of Subjects

The participation in this study may be stopped at any time by the study PI without the participant's consent because:

- The study Medical investigator thinks it necessary for subject's health or safety;
- Participant has not followed study instructions;
- The TRI has stopped the study; or
- Administrative reasons require the participant's withdrawal.

Subject Request for Withdrawal from Study

Participation in this study is voluntary. Participants may decide not to participate in this study or may withdraw from this study at any time without penalty or loss of benefits.

Data Collection and Follow-up for Withdrawn Subjects

Participants who request withdrawal or who are withdrawn by the PI from the study will have their data maintained in the research database. This data and biospecimens from the withdrawn participant may be included in subsequent analysis. Participant withdrawal of biospecimens is not an option.

Adverse Event Reporting

Adverse Events

An adverse event (AE) is defined as both an expected side effect that is of a serious nature, or an unexpected side effect/event regardless of severity. Each participant is evaluated for adverse events at every study visit. Any event that is reported to the study staff and which meets the criteria of an adverse event will be documented as such and graded as to its attribution (unrelated to protocol, or possibly, probably, or definitely related to protocol) and severity (mild, moderate, or severe).

Recording of Adverse Events

At each contact with the subject, the investigator will seek information on adverse events by specific questioning and, as appropriate, by examination. Information on all adverse events will be recorded immediately in the source document, and also in the appropriate adverse event module of the case report form (CRF). All clearly related signs, symptoms, and abnormal diagnostic procedures results will be recorded in the source document.

Notification of Adverse Events

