Adverse events will be reported according to AdventHealth IRB guidelines.

Safety Monitoring Plan

Safety Monitoring

Research and safety data will be reviewed by the PI. This review will take place at regular meetings with the clinical coordinator and medical investigator where the safety labs for each new subject will be reviewed. Other items discussed will include: progress or adverse events occurring in the following: subject confidentiality, subject recruitment, and consent

process. All will monitor response to tolerance of and effectiveness of the exercise program.

Progress reports, including patient recruitment, retention/attrition, and AEs from the reviews will be compiled into an annual report and will include a list and summarization of adverse events. In addition, the annual report will address (1) whether adverse event rates are consistent with pre-study assumptions; (2) reason for dropouts from the study; (3) whether all participants met entry criteria; (4) whether continuation of the study is justified on the basis that additional data are needed to accomplish the stated aims of the study; and (5) conditions whereby the study might be terminated prematurely. The annual report will be forwarded to the Advent Health IRB and the TRI.

Data and Safety Monitoring Board (DSMB) or Equivalent

A Data and Safety Monitoring Board (DSMB) will be assembled by the NIH Program and study investigators. The DSMB will meet at a regular cadence that will be decided by the members of the DSMB. The DSMB will provide oversight and monitoring to ensure the safety of participants and the validity and integrity of the data and will be empowered to provide recommendations related to all aspects of protocol integrity as well as factors affecting participant safety. We propose that the DSMB consist of members external to the institution, without conflicts of interest and with the following qualifications:

1. An expert in the science of exercise and effects of physical activity.
2. A physician who can lead the effort in monitoring the overall event rate of various adverse events (AE) and serious adverse events (SAE), as well as balance between intervention groups.
3. An external statistician who can monitor data collection, critique analysis plans, request additional data analysis, and provide interpretation of results to the DSMB members.

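### The Phase IV schedule asks about adverse events at all 16 visits in EX but at 3 to about 10 in CON, so minor unexpected events are more likely to be recorded in EX

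*Protocol*

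**What the plan says.** **Schedule.** In the Phase IV table (Ambulatory/Exercise Recovery), one mark means "only on this visit for exercise cohort" and another means "only on this visit for ambulatory cohort". The Adverse Events row has an entry at each of the 16 visits. Visits 1–3, 5–7 and 9–15 carry the exercise mark alone. Visits 4, 8 and 16 carry the mark that the same table gives to biopsy, DEXA and MR, which both arms undergo. The Vital Signs and Medication rows show the same pattern.

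**Contacts.** EX trains "3 days per week at the TRI exercise training facility" for four weeks. For the other arm, "Participants in the ambulatory recovery group will not receive any exercise intervention or advice on exercise". Apart from one follow-up telephone call after bed rest, no call or diary is described for CON during recovery.

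**General rule.** Under Adverse Event Reporting, "Each participant is evaluated for adverse events at every study visit", and "At each contact with the subject, the investigator will seek information on adverse events by specific questioning". An expected side effect counts as an AE only if it is serious. An unexpected event counts at any severity.

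**Use.** The section on the DSMB describes a physician member who follows AE and SAE rates "as well as balance between intervention groups". The DSMB also receives information split by randomized group in closed session.

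**The concern.** If one arm is asked every one to three days and the other about weekly or less often, short-lived events are more likely to be remembered and recorded in the first arm. With about 20 starters per group, a few extra recorded events can look like an imbalance. The DSMB might then see a harm of exercise that reflects questioning alone. It might also miss events in CON, which still has repeated biopsies and a clamp during recovery. Enquiries that were never made cannot be restored by a later analysis, so this has to be settled in the visit schedule.

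The table also disagrees with the general rule. CON has a biopsy, DEXA and MR at visit 12, and a VO2max test and 400 m walk at visit 15. The AE row marks both visits for EX only, although the rule calls for AE evaluation at every study visit.

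**Working it through.** The protocol gives no figure to reproduce here. The check counts the marks and then illustrates the possible size.

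**1. Enquiries in EX.** The exercise-only marks number 3 + 3 + 7 = 13, and there are 3 both-arm marks: 13 + 3 = 16. The Cardio and Strength rows show 12 training visits. So 12 of the 13 exercise-only AE marks fall on training visits, and the thirteenth is visit 12, where both arms have procedures.

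**2. Enquiries in CON, three readings.**
- As printed: visits 4, 8 and 16, so 3.
- With a lost mark restored at visit 12: 4.
- With the every-visit rule applied to all visits that have a procedure read as applying to CON (1, 3, 4, 5, 8, 12, 13, 14, 15, 16): about 10.

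The superscripts are damaged in the text at hand, so the choice between these readings is uncertain. EX exceeds CON in all three.

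**3. Timing.** Using the table's day-of-week row, with visit 1 as day 0, visit 16 as day 28 and visit windows ignored:
- EX: gaps of 1 to 3 days (five of 3 days, three of 2, seven of 1; 15 + 6 + 7 = 28).
- CON as printed: days 6, 13 and 28, so the last two visits are 15 days apart.
- CON with visit 12: days 6, 13, 20 and 28.
- CON with all its visits: days 0, 4, 6, 7, 13, 20, 21, 24, 25 and 28, with a longest gap of 7 days.

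**4. Illustration (assumed model, not in the protocol).** True event rates are equal and constant over 28 days. The chance that an event is still reported halves every *h* days until the next enquiry. For gaps g before each enquiry,

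fraction recorded = [h / (28 ln 2)] × Σ(1 − 2^(−g/h)).

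For h = 7 the factor is 7 / (28 × 0.6931) = 0.3607.
- EX: 0.3607 × (5 × 0.2570 + 3 × 0.1797 + 7 × 0.0943) = 0.3607 × 2.484 = 0.90.
- CON as printed, gaps 6, 7 and 15: 0.3607 × (0.4480 + 0.5000 + 0.7736) = 0.3607 × 1.722 = 0.62.
- Ratio: 1.44.

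The fraction recorded in EX is 0.78, 0.90 and 0.95 for h = 3, 7 and 14 days. For CON (ratios from unrounded fractions):

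| CON reading | Enquiries | Fraction recorded, h = 3 / 7 / 14 | EX:CON ratio, h = 3 / 7 / 14 |
|---|---|---|---|
| As printed | 3 | 0.39 / 0.62 / 0.77 | 2.01 / 1.44 / 1.22 |
| Visit 12 added | 4 | 0.49 / 0.72 / 0.84 | 1.58 / 1.25 / 1.12 |
| All CON visits | about 10 | 0.64 / 0.81 / 0.90 | 1.22 / 1.10 / 1.05 |

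**5. With the same enquiry days in both arms** the two sums are identical, so the ratio is 1.00 for every h.

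**The case against.** The case against has several good points.

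- **More contact is inherent in the design.** Supervised training compared with usual routine cannot have equal visit counts, and asking about AEs at training is ordinary safety practice. This stands. The point is not to ask less in EX, but to have a common basis for comparing arms.
- **No formal between-arm AE test is stated.** The phrase on balance comes from the proposed qualifications of a DSMB member, and the DSMB will know that EX attends sessions. This also stands and limits the consequence to safety oversight. That oversight is nevertheless meant to look at the arms side by side.
- **The AE definition removes expected, non-serious effects.** Much minor training or biopsy soreness would not count. What remains exposed is the minor unexpected event.
- **Tabulation usually belongs in the SAP, which is not shown.** This is true of the table layout. The visits at which CON is asked are fixed in the protocol, and here the protocol disagrees with itself.
- **The remedy is imperfect.** EX participants questioned at sessions may recall better at the common visit, and a table of common enquiries could set aside events caused by exercise. Hence the separate table in the fix.

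Two stronger readings are tempting. A reader might infer that AE counts as a whole cannot be compared between arms. The documents do not support that: serious events are unlikely to be missed at CON's contacts, and expected non-serious effects are not counted. A reader might also attach one figure, for example 90% reporting in EX against 50% in CON, giving 0.9 / 0.5 = 1.8. The protocol contains no reporting probabilities. The value lies above the whole range for weekly CON enquiry in the table (1.12 to 1.58), and far above it if CON is asked at all its visits (1.05 to 1.22).

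**Conclusion.** The concern holds in a limited form. The schedule builds in unequal AE enquiry during recovery: 16 occasions in EX against 3 in CON as printed, 4 if a visit 12 mark was lost, and about 10 if the every-visit rule governs. The direction is the same under every reading, with minor unexpected events more likely to be recorded in EX at equal true rates. The size cannot be derived from the protocol. The range of roughly 1.05 to 2.0 rests on an assumed recall half-life of 3 to 14 days and on how the damaged table marks are read.

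Separately, and without any model, the AE row conflicts with the Adverse Event Reporting section at visits 12 and 15. The two must be reconciled. The primary outcomes are not affected. The matter should be corrected because the correction is cheap and cannot be made after the data are collected.

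**What to change.** 1. Reconcile the Phase IV AE row with Adverse Event Reporting by marking AE enquiry for both arms at every visit CON already attends, and at least at visits 4, 8, 12 and 16.
2. At those visits use one scripted question in both arms, covering the time since the last common visit.
3. For the DSMB's between-arm view, tabulate AEs from these common enquiries. An EX event already reported at a session counts if it is reported again at the common visit.
4. List AEs noted only at training sessions in a separate flagged table, next to the number of contacts per arm, so that nothing seen in EX is lost from view.
5. Leave safety questioning at training sessions unchanged.

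The cost is a short script, corrected marks in one table row and one extra safety table. No visit or procedure is added. Some prompting of recall by session questioning will remain in EX, so the comparison becomes fairer without becoming perfectly even.
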